11. STUDY PROCEDURES

11a. Recruitment of participants

Screening will take place before consent. The respiratory physician involved in the study will approach potential study participants within 24 hours of admission for a primary diagnosis of AECOPD. If they fulfill inclusion criteria and have no exclusion criteria they will be invited to participate in this study. They will be provided with written information about the research and given the opportunity to ask questions regarding participation. The participant will have up to 2 hours to decide if they wish to participate. Once informed consent is given they will be considered participants. We aim to recruit 80 participants. From a small audit (10 patients) performed in 2017 we expect that 60% of patients asked to participate will be able perform FeNO and spirometry testing essential for recruitment. Those who cannot complete either FeNO or spirometry will be excluded from final analysis as they cannot contribute to the primary outcome. However, as this is a potential source of bias we will collect all other data and follow-up outcomes from these patients also. We expect 12 months will be necessary to recruit 80 patients who can perform both FeNO and Spirometry on admission.

11b. Randomisation

This is a prospective observational cohort study. No randomization is required. No case matching is required.

11c. Study procedure

We will approach potential study participants within 24 hours of admission for a primary diagnosis of AECOPD. If they fulfill inclusion criteria and have no exclusion criteria they will be asked to participate in this study. Once informed consent is given they will be considered participants. Patient questionnaire, FeNO and spirometry testing will be performed at Day 1 (recruitment day) and at 6-week follow-up appointment. A further questionnaire via phone contact will be performed at 3, 6, 9 & 12 months. If the participant cannot be contacted by phone, the study will contact the nominated next-of-kin and general practitioner. The patient's general practitioner will be informed of study participation. This study does not involve any treatment intervention. All additional tests, except FeNO measurement, are considered part of usual care. Additional tests include spirometry and blood testing (FBC, IgE and RAST) and will be used to identify individuals who may have Asthma COPD Overlap Syndrome (ACOS). These tests can be "added on" to bloods taken on admission. The study does not

require additional follow-up appointments as the 6 week follow-up of these patients is part of usual care. An extra phone contact with the patients will be made at 3, 6, 9 & 12 months.

Day one:

- Location: SJOG hospital medical ward inpatient room
- Duration: 30 minutes
 - Informed Consent 10 minutes
 - Questionnaire 5 minutes
 - FeNO testing 5 minutes
 - Spirometry testing 10 minutes
- Baseline data collection form
 - Questionnaire
 - patient demographics, Charlson Comorbidity Index, COPD Assessment test, modified MRC dyspnea scale, Hospital Anxiety and Depression Scale
 - Laboratory blood tests
 - Full blood picture as per usual medical care. Retrieved from hospital pathology program.
 - IgE and RAST testing added This is usual clinical care to identify individuals who may have ACOS.
 - o Radiology CXR as per usual medical care. Retrieved from hospital radiology program
 - Treatment as per usual medical care documented from hospital patient medical file
- FeNO bedside measurement
- Spirometry testing

Early Post-Hospital Discharge:

• Researcher staff only – interrogating electronic medical records to determine discharge date and corticosteroid medication prescriptions during and after hospitalization.

6 week follow-up:

- Location: SJOG hospital medical outpatient clinic
- Duration: 30 minutes
 - o Questionnaire 5 minutes. (COPD Assessment test, modified MRC dyspnea scale)
 - FeNO testing 5 minutes
 - Spirometry testing 10 minutes
 - Blood testing 10 minutes
- 6 week data collection form
- Laboratory blood tests FBC, CRP, IgE
- FeNO bedside measurement
- Spirometry testing

3,6,9 & 12 month follow-up:

- Location: Phone contact only
- Duration: 5 minutes
 - Questionnaire 5 minutes
- 3, 6, 9 &12 month data collection form

• If the patient is unable to be contacted, consent will have been obtained to contact the nominated next of kin and General Practitioner to obtain any hospital admission discharge summary to determine the primary outcome.

11d. Measurement tools used

Fraction of Expired Nitric Oxide

FeNO measurement will be performed using the NIOX VERO® device. It is able to measure expired nitrous oxide within a range of 5 to 300 ppb (accuracy +/- 5 ppb of measured values ≤ 50 ppb). NIOX devices are the most widely used devices for measuring airway inflammation in clinical practice and clinical studies. It requires the patient to exhale at a constant rate for at least 10 seconds, which some patients may find difficult to perform. It provides a measurement of expired NO within 60 seconds of test. It is portable and battery powered and thus suitable for ward and clinic environments.

Spirometry

- Spirometry will be performed as per ATS guidelines (Miller et al., 2005) with the EasyOne Spirometer® device. Measures recorded include FEV1, FVC and FEV1/FVC ratio. Both measured values and percent of predicted values will be recorded. Presence and severity of airflow obstruction will be classified as per GOLD spirometry criteria.
- The EasyOne Spirometer®, has been chosen because it provides a high degree of accuracy, robustness, portability, and ease of storage. It can be used easily on the ward and in the clinic environment, it operates on batteries and requires no calibration. It has been previously used in other studies.

COPD Assessment Test (CAT)

- The CAT is a patient-completed instrument that can quantify the impact of COPD on the patient's health. Validation studies have shown that it has properties very similar to much more complex health status questionnaires such as the St George's Respiratory Questionnaire. Systematic reviews confirm that the CAT provides reliable measurement of health status and is responsive to change with treatment and exacerbations. Since 2013 it has been incorporated as the preferred measure of symptomatic impact of COPD into clinical assessment schemes and is also included in the COPD Foundation guide.
- The test is comprised of eight questions pertaining to cough, sputum, chest tightness, exercise tolerance, ability to perform activities of daily living, confidence in leaving the home, sleep and energy levels. Each question is scored on a 6-point scale (0 to 5) yielding a total possible score of 40 for the questionnaire. The total CAT score provides a broad clinical picture of the impact of COPD on an individual patient with scores of >30, 21-30, 10-20 and <10 corresponding to very high, high, moderate and low impact respectively. A total score of 5 is the upper limit of normal in a healthy non-smoker(Jones et al., 2011). A systematic review (Gupta et al., 2014) that included 36 studies carried out in 32 countries reported the CAT to be reliable, valid and responsive as more complex HRQoL instruments.

- Although the minimum clinically important difference in the total CAT score is unclear, CAT scores in patients with moderate-severe exacerbations are

approximately 5 units higher than in those who have stable COPD. Patients responding to treatment for their exacerbation have been shown to reduce their CAT score by 2 units in 14 days.

- Modified MRC (mMRC) dyspnea scale
 - o mMRC dyspnoea scale quantifies the effect of breathlessness on daily activities (Celli et al., 2004). The test comprises five statements that describe almost the entire range of respiratory disability from none (Grade 1) to almost complete incapacity (Grade 5). It can be self-administered by asking subjects to choose a phrase that best describes their condition. All the questions relate to everyday activities and are generally easily understood by patients. A score can usually be obtained in a few seconds. The MRC breathlessness scale does not quantify breathlessness itself. Rather, it quantifies the disability associated with breathlessness by identifying that breathlessness occurs when it should not (Grades 1 and 2) or by quantifying the associated exercise limitation (Grades 3–5).
 - There is up to 98% agreement between observers recording MRC breathlessness scores. The score correlates well with the results of other breathlessness scales, lung function measurements and with direct measures of disability such as walking distance. Its main disadvantage over other more complex scales is its relative insensitivity to change. Changes can be demonstrated, for example, after lung surgery but it is uncommon for individuals to improve or deteriorate by an entire grade over relatively short periods.
 - The MRC breathlessness scale is widely used to describe patient cohorts and stratify them for interventions such as pulmonary rehabilitation in COPD. It can predict survival and it is advocated as complementary to FEV1 in describing disability in those with COPD.
- Charlson Comorbidity Index (CCI)
 - The CCI predicts the one-year mortality for patients with a range of co-morbid conditions. Each of 22 comorbidities is assigned a score of 1, 2, 3 or 6 depending on the risk of death. The sum of the score predicts mortality and is adjusted for age. It has been extensively validated and used in numerous trials.
 - https://www.mdcalc.com/charlson-comorbidity-index-cci
- Hospital Anxiety and Depression Scale (HADS)
 - Anxiety has previously been linked to hospital readmission for COPD. The HADS is a 14 question, self-administered survey focusing on both anxiety and depressive symptoms. It is scored ordinally. It has been extensively validated and is recommended by the National Institute for Health and Care Excellence as a tool to diagnose depression and anxiety.
- Questionnaire
 - Demographic, smoking history, hospital admission history
- Medication Chart
 - Usual medication and acute pharmacotherapy information
- Observation chart
 - Assessment of admission physical observation including temperature, respiratory rate, pulse rate, blood pressure
- Biological specimens
 - o Full blood count to assess eosinophil blood count. At day 1 and 6 week follow-up.

- o IgE level. At day 1 and 6 week follow-up.
- o RAST dust mite, pollen and grass mix, animal epithelia mix, mould. At day 1 only.

11e. Safety considerations/Patient safety

This observational study does not involve any treatment interventions. Treatment decisions will be managed by the treating physician, in cooperation with the patient, independently of the study and its researchers. At SJOG Midland, treating physicians are specialist general physicians who are independent of the study personnel, minimizing conflict or duality of interest between treating doctors and the study team. All tests performed, except the measurement of FeNO, are considered part of usual care. The additional FeNO measurement using the NIOX VERO® device can be difficult for some patients to perform, especially when they are acutely unwell. Therefore, despite the test being very safe it may cause some minor distress to some patients.

Administering the research questionnaire may have adverse psychological effects on susceptible individuals. Particularly questions pertaining to their level physical functioning and regarding the presence of anxiety or depression symptoms.

Any adverse events of the test or questionnaire will be recorded and reported to the treating physician with the participant's consent.

11f. Data monitoring

Patient questionnaires and CRFs will be stored in a locked filing cabinet in a secure medical office of Midland Physician Service at St John of God Hospital Midland. Only staff involved in the study will review these forms.

Data will be entered in a computer spreadsheet in a de-identified form. This password protected spreadsheet will be saved in a password protected personal computer. Only staff involved in the study analysis will review these forms.

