4. OBJECTIVES

The objectives of the study are:

- 1. To determine if FeNO levels measured in the first 24 hours of admission to hospital for an AECOPD correlates to readmission risk at 12 months (and time to readmission).
- 2. To determine if FeNO levels measured in the first 6 weeks after discharge from hospital for an AECOPD correlates to readmission risk at 12 months (and time to readmission).
- 3. To determine if FeNO levels measured in the first 24 hours of admission to hospital for an AECOPD predict FEV1 improvement at 6 week follow-up.
- 4. To determine if FeNO levels measured in the first 24 hours of admission to hospital for an AECOPD predict CAT improvement at 6 week follow-up.
- 5. To describe the relationship between FeNO levels measured in the first 24 hours of admission to hospital for an AECOPD and blood eosinophil count.
- 6. To describe changes in FeNO levels between the first 24 hours of admission to hospital for AECOPD and at 6 week follow-up.

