8. STUDY POPULATION

The study population is consecutive patients admitted to St John of God Midland Private and Public hospital with a primary diagnosis of severe acute exacerbation of COPD (AECOPD). An AECOPD is defined as acute worsening of respiratory symptoms that results in additional therapy: antibiotics and/or systemic corticosteroids. Admission to hospital usually implies severe exacerbation of COPD. As this is an exploratory study a total of **80** patients will be recruited.

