12. STATISTICAL CONSIDERATIONS AND DATA ANALYSIS

12a. Sample size and statistical power

This is an observational study without a pre-specified sample size. Based on pilot data and numbers of COPD admissions, we anticipate 80 participants will be both feasible and sufficient to examine the primary outcome.

12b. Statistical methods

Predictors for the primary outcome (readmission for COPD exacerbation) will be identified by using a multivariate logistic regression model incorporating FeNO level and other known and suspected factors associated with COPD readmissions. Associations between FeNO and readmission will be presented as odds ratios. Systemic steroids can affect FeNO measurements. Therefore, outcomes will also be analysed by dose of systemic corticosteroid prior to FeNO measurement.

Predictors of the secondary outcomes (time to readmission for repeat exacerbation of COPD and time to repeat exacerbation) will be identified by using a Cox Proportional Hazards regression model or logistic regression model as appropriate incorporating FeNO level and other known and suspected NORAD Protocol V1.2

March 2018

factors associated with COPD readmissions. Associations between FeNO and readmission will be presented as hazard ratios (Cox Proportional Hazards model) or odds ratios (logistic regression model).

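### Section 11a bars patients who fail the admission FeNO or spirometry from the whole final analysis, but its stated reason does not hold for Objective 2, which needs only the 6-week FeNO and readmission

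*Protocol*

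**What the plan says.** Protocol section 11a sets the rule and gives its reason in one sentence: "Those who cannot complete either FeNO or spirometry will be excluded from final analysis as they cannot contribute to the primary outcome". That sentence names neither a time point nor an objective. The paragraph ends with "We expect 12 months will be necessary to recruit 80 patients who can perform both FeNO and Spirometry on admission", which places the tests on admission and shows that both must be completed.

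The sentence after the rule concedes that the exclusion may introduce bias and adds: "we will collect all other data and follow-up outcomes from these patients also". It does not return these patients to any analysis.

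Section 4 gives Objective 2 as: "To determine if FeNO levels measured in the first 6 weeks after discharge from hospital for an AECOPD correlates to readmission risk at 12 months". The primary hypothesis in section 5 likewise covers FeNO on admission, at 6 weeks, or both. Section 10a takes the primary outcome, readmission for COPD, from the discharge summary. Section 11c schedules FeNO at Day 1 and again at the 6-week visit. Section 11e says of the FeNO test that it "can be difficult for some patients to perform, especially when they are acutely unwell".

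**The concern.** An exclusion triggered by the admission tests is applied to an objective that does not use the admission FeNO. The justification is that non-completers cannot contribute to the primary outcome. But readmission needs no breath test, so what these patients lack is the Day 1 exposure. Objective 2 has its own exposure, measured about six weeks later.

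Two things are at stake. One is precision: pairs of 6-week FeNO and readmission that could be had at almost no cost are kept out of a small study. The other is selection: section 11e ties difficulty with the test to acute illness, so failure on Day 1 is plausibly related to acute severity and may have resolved by 6 weeks. Objective 2 would then be estimated only in patients well enough to do the manoeuvre on admission, although its question concerns patients after discharge.

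**Working it through.** **What each objective needs**

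| Objective | FeNO needed | Other data needed |
|---|---|---|
| 1 | Day 1 | 12-month readmission |
| 2 | 6 weeks | 12-month readmission |
| 3, 4 | Day 1 | change in FEV1 or CAT to 6 weeks |
| 5 | Day 1 | blood eosinophil count |
| 6 | Day 1 and 6 weeks | none |

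Only Objective 2 can be answered without a Day 1 FeNO. The exclusion in 11a is sound for a Day 1 FeNO failure in Objectives 1 and 3-6, and unsupported for Objective 2.

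**Inputs from the protocol**
- Target: 80 (section 8: "As this is an exploratory study a total of 80 patients will be recruited").
- Share able to do both tests: 60% (section 11a: "we expect that 60% of patients asked to participate will be able perform FeNO and spirometry testing essential for recruitment"), based on an audit of 10 patients.
- There is no power calculation to reproduce; section 12a says "This is an observational study without a pre-specified sample size".

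**Number falling under the exclusion**
- Patients asked: 80 / 0.60 = 133.3.
- Non-completers: 133.3 - 80 = 53.3.

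The 60% applies to patients asked, not to those who consent, so 53 is an upper bound reached only if everyone consents. If the audit result was 6 of 10, the exact (Clopper-Pearson) 95% interval is 26% to 88%. The same arithmetic then gives 80/0.262 - 80 = 225 non-completers at one end and 80/0.878 - 80 = 11 at the other.

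**Patients Objective 2 could gain**

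Two assumptions, neither in the protocol: *f*, the share of non-completers who failed on FeNO and otherwise meet the entry criteria; and *s*, the share of those who can do FeNO at 6 weeks. Each is set at 50%, with a range of 25% to 75%.

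Gain = 53.3 × *f* × *s*
- Central: 53.3 × 0.50 × 0.50 = 13.3
- Low: 53.3 × 0.25 × 0.25 = 3.3
- High: 53.3 × 0.75 × 0.75 = 30.0

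**Effect on precision**

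With a similar spread of FeNO and a similar readmission rate in the added patients, the width of the interval for the log odds ratio scales with 1/√n:
- Central: √(80/93.3) = 0.926, about 7% narrower
- Low: √(80/83.3) = 0.980, about 2% narrower
- High: √(80/110) = 0.853, about 15% narrower

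These counts assume that everyone attends at 6 weeks. If attendance is lower but equal in both groups, the counts shrink and the percentages do not: at 80% attendance the central case is 64 + 10.7, and √(64/74.7) is again 0.926.

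**The case against.** **The scope of the rule is inferred.** The exclusion sentence is loose, and its reason could be read as confining it to the primary analysis. Assigning analysis sets to objectives is also often left to the SAP. The looseness is real, but the text says final analysis and makes no exception, and the 6-week FeNO is itself part of the primary hypothesis. The point is also not an omission: the protocol states a rule and supports it with a reason that is wrong for one objective. If the 6-week test is not attempted in these patients, no SAP can recover it.

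**The protocol already deals with the bias.** It names the problem and keeps collecting data, and section 11c could be read as scheduling the 6-week FeNO for every consented participant. That deserves credit, but collection alone does not undo the exclusion. Whether the remaining data to be collected include a 6-week FeNO is not settled. The loss is therefore conditional: pairs are discarded if the test is done, and never created if it is not.

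**One cohort with both admission tests is defensible.** It lets admission and 6-week FeNO be compared in the same patients. This stands, and is why the restricted analysis should be kept alongside the wider one.

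**A stronger reading is tempting:** that the rule throws out the sickest, most breathless patients, who are the most likely to be readmitted. The documents do not support it. Section 11a gives no reason for test failure, section 11e supports only some link with acute illness, and patients needing ventilation or inotropic support are already excluded by section 9b. Inability to do a breath test is not among the readmission risk factors listed in the background. Neither the direction nor the size of any bias can be derived.

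**Conclusion.** The point holds in a limited form. The exclusion is justified for the objectives that use the Day 1 FeNO. It is not justified for Objective 2 or the 6-week part of the primary hypothesis, because a Day 1 FeNO non-performer with a valid 6-week FeNO has everything the analysis needs.

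The gain is modest: about 13 patients (3-30) and an interval about 7% (2-15%) narrower. It rests on the 60% from a 10-patient audit, on full consent, and on two assumed shares. The selection effect is plausible but cannot be quantified. The argument covers failure on FeNO; a patient with no spirometry showing airflow obstruction may not meet the entry criteria at all. The change is worth making because it is cheap, bears on the primary hypothesis, and cannot be made once the 6-week visits have passed.

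**What to change.** Reword section 11a so that test completion is required by objective:
- Objectives 1 and 3-6: a valid Day 1 FeNO, plus the other measurements each one uses.
- Objective 2: every consented participant who meets the entry criteria, including a documented FEV1/FVC below 70%, and has a valid 6-week FeNO, whatever the Day 1 FeNO result.

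State in section 11c that FeNO is attempted at 6 weeks in participants who could not do it on Day 1. Report Objective 2 a second time restricted to Day 1 performers, so that it can be set beside Objective 1 in the same kind of patient.

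The cost is a change of wording and a 5-minute test at a visit that is already usual care. The drawback is that Objectives 1 and 2 then rest on slightly different sets of patients, which the restricted analysis makes visible.

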9. ELIGIBILITY CRITERIA

9a. Inclusion criteria

- Age ≥ 40 years
- Smoking history ≥ 15 pack years
- Suspected or Known COPD defined as a FEV1/FVC ratio of <70% on spirometry
- Hospital admission with primary diagnosis of AECOPD

9b. Exclusion criteria

- Patients who do not have airflow obstruction on spirometry (FEV1/FVC<70%)
- Patients in acute respiratory failure requiring non-invasive positive pressure ventilation or invasive mechanical ventilation
- Patients requiring ionotropic support
- Patients with concurrent diagnosis of bronchiectasis, interstitial lung disease, pulmonary embolism or acute cardiac failure
- Overseas and Interstate visitors

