10. STUDY OUTCOMES

10a. Primary Outcome

 Hospital re-admission for COPD within 12 months defined as admitted to hospital, excluding emergency department presentation only, with discharge diagnosis on the discharge summary being "Exacerbation of COPD".

10b. Secondary Outcome(s)

- Time to hospital re-admission for COPD (up to 12 months)
- Repeat exacerbation of COPD within 12 months, defined as an acute worsening of respiratory symptoms that results in increased dose of systemic corticosteroids and /or antibiotics. This outcome will be self reported.
- Change in FeNO levels between Day 1 of admission and on follow-up visit at 6 weeks.
- Change in FEV1, FVC, FEV1/FVC between Day 1 of admission and on follow-up visit at 6 weeks.
- Change in CAT score between Day 1 of admission and on follow-up visit at 6 weeks.

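### Section 11a drops patients with a valid Day-1 FeNO and documented obstruction for want of Day-1 spirometry, on a reason that is wrong for them

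*Protocol*

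**What the plan says.** Section 11a sets the analysis population and gives its reason: "Those who cannot complete either FeNO or spirometry will be excluded from final analysis as they cannot contribute to the primary outcome". It then recognises the risk and keeps the data: "as this is a potential source of bias we will collect all other data and follow-up outcomes from these patients also". Taken alone, the word 'either' could mean failing one test or failing both. The end of the same section settles it: "We expect 12 months will be necessary to recruit 80 patients who can perform both FeNO and Spirometry on admission". Failing one test is enough for exclusion.

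The primary outcome in section 10a has no spirometric component: "Hospital re-admission for COPD within 12 months defined as admitted to hospital, excluding emergency department presentation only". Section 11c obtains it by telephone follow-up and, where the patient cannot be reached, through the next of kin and "General Practitioner to obtain any hospital admission discharge summary to determine the primary outcome". Objective 1 in section 4 reads: "To determine if FeNO levels measured in the first 24 hours of admission to hospital for an AECOPD correlates to readmission risk at 12 months".

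Spirometry also enters as an inclusion criterion in section 9a: "Suspected or Known COPD defined as a FEV1/FVC ratio of <70% on spirometry". Section 9b repeats the requirement as an exclusion.

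**The concern.** The rule joins two tests that do different work. FeNO is the exposure in the primary question. Day-1 spirometry is the baseline for the change in FEV1, FVC and their ratio, and possibly a severity covariate in the readmission model. Requiring both tests for every analysis removes patients who have all that the primary question needs, and the stated reason does not describe them.

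Two things are at stake. The primary analysis set is smaller than it need be, in a study of only 80. It is also selected on the ability to perform spirometry during an acute admission, so the result applies to a narrower group than the patients in whom FeNO could be measured. The protocol sees this risk and collects the outcomes that would let it be examined, but then bars these patients from the final analysis.

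**Working it through.** **1. Does the reason fit? What each non-completer has for objective 1**

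| Patient on Day 1 | FeNO (exposure) | 12-month readmission (outcome) | Does the reason in 11a fit? |
|---|---|---|---|
| FeNO valid, no spirometry, obstruction already documented | yes | collected | No |
| FeNO valid, no spirometry, obstruction never confirmed | yes | collected | No, but eligibility under section 9 is unconfirmed |
| No FeNO, with or without spirometry | no | collected | In substance yes: outcome present, exposure absent |

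The first row is the group at issue. Section 2 lists severity of airflow obstruction as a readmission risk factor, and section 12b allows such factors into the logistic model. Day-1 FEV1 may therefore be a covariate, but its absence leaves a gap in a covariate and not in the outcome. Of the six objectives in section 4, only objective 3 (FEV1 improvement) needs spirometry as a variable.

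**2. How many patients could be involved?**

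Inputs: 80 completers (sections 8 and 11a) and 60% of patients asked able to do both tests, from an audit of 10 (section 11a). The 80 cannot be reproduced, because section 12a gives no alpha, power, effect size or event rate and rests it on feasibility.

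- Patients asked: 80 / 0.60 = 133.3, about 133.
- Non-completers: 133 − 80 = 53. This is an upper figure, because the 60% applies to patients asked, and anyone who declines is not followed.
- Uncertainty in the 60%: for 6 of 10, the exact 95% interval is 26.2% to 87.8%. Patients asked then range from 80 / 0.878 = 91 to 80 / 0.262 = 305, and non-completers from about 11 to about 225.

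**3. What would keeping them add?**

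The protocol does not say how many non-completers fail spirometry alone. Call that number k and assume a share of the 53. With the same number approached, and a similar readmission rate and FeNO spread, the standard error of the FeNO term relative to N = 80 is about √(80 / (80 + k)).

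| Assumed share | k | N | Relative SE |
|---|---|---|---|
| 10% | 5 | 85 | √(80/85) = 0.97 |
| 25% | 13 | 93 | √(80/93) = 0.93 |
| 50% | 27 | 107 | √(80/107) = 0.86 |

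These are best-case gains, since a patient with imputed FEV1 carries somewhat less information than one with it measured.

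**The case against.** The strongest reply is that spirometry is more than a covariate. It defines the disease in section 9, section 11a treats both tests as essential for recruitment, and section 11d classifies obstruction from study spirometry. A suspected case with no spirometry at all has unconfirmed eligibility, and leaving that patient out is defensible. This stands, and the point is limited accordingly. It does not cover known cases with obstruction already on record. Section 11a puts screening before consent and the Day-1 tests after it, so a failed Day-1 test does not show that a patient is ineligible.

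The group may also be small. Sections 11d and 11e describe FeNO as the manoeuvre that patients may find difficult and say nothing similar of spirometry. This stands too, and is why the range starts at 10%.

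A reader might infer that some 53 followed patients are wrongly discarded. The protocol does not support that: the figure counts patients asked, and it includes FeNO failures, who cannot enter a model of FeNO.

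A reader might also infer that the FeNO odds ratio is biased. Selecting on baseline test ability mainly limits generalisability and does not by itself bias an adjusted odds ratio. That patients unable to do spirometry are sicker and more often readmitted is plausible, but the protocol does not show it.

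Finally, how missing data are handled may properly be left to an analysis plan. The exclusion and its reason, however, are stated outright in the protocol, and an analysis plan that followed them would carry the error forward.

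**Conclusion.** The point holds for consented patients with a valid Day-1 FeNO and obstruction documented at or before Day 1 but no usable Day-1 spirometry. For them the reason in section 11a contradicts sections 4, 10a and 11c and the sentence that follows it in 11a. The result is an unnecessarily small and selected primary analysis set.

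The size is uncertain. At 60% completion, an assumed spirometry-only share of 10% to 50% returns about 5 to 27 patients. The standard error falls by about 3% to 14% at best, provided that the same number is approached and that obstruction was already documented in those patients. The error in the reason does not depend on these figures. In an exploratory cohort this is a moderate matter: worth correcting, but not one that invalidates the study.

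**What to change.** Reword section 11a, and align section 12b, as follows:

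- The primary FeNO–readmission analysis includes all consented, eligible patients with a valid Day-1 FeNO.
- Eligibility under section 9 rests on spirometry available at or before Day 1. The 6-week visit should not be used for this, because it would select patients on survival and attendance after baseline.
- Day-1 spirometry is required only for the FEV1, FVC and FEV1/FVC outcomes.
- Where FEV1 is a covariate in the readmission model, its absence is treated as a missing covariate, for example by multiple imputation.
- Twelve-month readmission is reported in performers and non-performers, from the outcomes already collected. Weighting by the inverse probability of completing the tests is optional.

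The cost is a little extra analysis and the retrieval of earlier spirometry where it exists, which the Day-1 data list in section 11c does not now include. No further follow-up is needed.
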